13. THE INTERVENTION

Patients in the MAC arm will still access TAU, alongside the MAC intervention. However, our PDG indicated that YP in the MAC arm received less mental health intervention than those randomised to TAU (PDG Competition 25 Panel B Programme Development Grants Final Report Form Project Title A Combined Mindfulness-Based Approach for Adolescent Non-Responders to First-Line Treatments of Depression or Anxiety and Their Carers: Establishing Feasibility of Implementation and Delivery Reference Number NIHR201024 Contracting Organisation Cambridgeshire and Peterborough NHS Foundation Trust Approved Duration 12 Current Duration 16, n.d.), and we expect to find similar results during the current study.

Figure 3: Logic model for the mechanisms of actions of the MAC intervention.

Logic Model for the mechanisms of action of the Mindfulness for Adolescents and Carers (MAC) intervention

RISK FACTORS

PROGRAMME COMPONENTS & MODALITIES

YOUNG PEOPLE (YP):

- Dysfunctional thinking style and attitudes, including rumination and self-blame
- Thought suppression
- Aversion and avoidant coping
- Impulsivity

YP PROGRAMME: Aims to give YP the understanding and skills that will enable them to recognise negative states of mind, and to step out of habitual patterns of thinking, acting and feeling that are reactivated by low mood and anxiety.

PARALLEL CARER PROGRAMME: Aims to give carers the same understanding and skills to support their child to step out of habitual patterns of thinking, acting and feeling, as well as to improve family relationships.

- Intentional attention: Recognising mind wandering. Anchoring of attention on present moment/ experience
- Introspective awareness: Recognising habitual patterns of reactivity, and associated aversion/ judgements
- Meta-cognitive awareness (Decentering): Developing new ways of 'being' and relating to thoughts and feelings.

Programme modalities: specific strategies and methods used to accomplish goals Body scan; Focussed attention mediations, such as those with focus on breath, body, or sounds; Observing distractions during meditations; Noticing and observing body sensations, thinking processes and feeling states in formal and informal mindfulness practices; Allowing and letting be (acceptance) exercises; Meditations to observe difficult experiences; Inquiry; Activities; Homework.

OUTCOMES

YOUNG PEOPLE:

- Improved emotional regulation
- Reduced reaction to stress
- Reduced psychological distress and anxiety

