Session checklists

Competence and fidelity will be assessed by applying the MBI-TAC (R. S. Crane et al., 2012) to video recordings of the weekly sessions. Attendance will indicate dosage received by YP and parents. In addition, session checklists will be used to record if all elements of a session were delivered as intended.

Summary of TAU

Young people, carers and practitioners strongly recommended TAU as the optimal comparator during extensive discussion in the feasibility work and PDG. In contrast to common assumptions, TAU was also the most potent comparator (smaller effect sizes) compared to active and waiting-list controls in a recent meta-analysis of psychological interventions for children over five decades (Weisz et al., 2017).

The characterisation of TAU was part of our PDG. The electronic case-record audit found that young people with depression attending CAMHS in Cambridge and London were typically girls, and commonly had comorbidities, particularly anxiety. Most referrals came from primary care, though many also were through Accident and Emergency Departments. Most young people received weekly therapy, commonly Cognitive Behavioural Therapy (CBT), but also Supportive, Family, and Interpersonal Therapies. Total time spent in the service was variable, but in some cases exceeded two years. Most young people were discharged because their treatment had been completed, often back to primary care. These results echoed an earlier audit of care pathways in Devon. The PDG found a consistent pattern of clinical pathways from young people, parents and case managers about the care pathway and TAU, despite significant variability across and within sites (Figure 4;) (PDG Competition 25 Panel B Programme Development Grants Final Report Form Project Title A Combined Mindfulness-Based Approach for Adolescent Non-Responders to First-Line Treatments of Depression or Anxiety and Their Carers: Establishing Feasibility of Implementation and Delivery Reference Number NIHR201024 Contracting Organisation Cambridgeshire and Peterborough NHS Foundation Trust Approved Duration 12 Current Duration 16, n.d.). The TAU arm received more treatment, including Family Therapy and Interpersonal Therapy than those in the MAC arm. Clinicians often continued with less frequent "check ins" and psychiatric medication reviews as needed with young people allocated to MAC.

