Interviews with case-managing clinicians highlighted areas where the services received by young people differed from the organisational offer described by services. While there was significant variation in the specific support offered to young people, general Supportive Therapy, CBT, and Systemic Family Therapy were common first line treatments. The most commonly reported treatment in interviews was Supportive Therapy, which was confirmed by data from the Treatment Recording Sheet (TRS). The typical referral and treatment pathway that was found during the PDG is summarised in **Figure 4:** Typical CAHMS pathway.

We will not be controlling or changing the participants' TAU, we have requested from sites that both arms be offered their usual care, regardless of being in this trial.

Figure 4: Typical CAMHS pathway

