The EQ-5D-5L (Rabin & Charro, 2001) describes health status in 5 health dimensions, with 5 levels of each. The patient reports their present health state by ticking the level of each dimension that currently applies to them. They then rate their current health state from 0-100 (best possible health state). This measure has good convergent and divergent validity with other health questionnaires (J. A. Johnson & Pickard, 2000).

Treatment Recording Sheet TRS; (Bearsley-[name] et al., 2008)

We will also measure public and charitable sector services accessed and health-related quality of life for both young people and carers for economic evaluation. Researchers will support practitioners to complete the revised TRS (Bearsley-[name] et al., 2008) (**Appendix L**) for any other therapy or psychological intervention provided, to allow for comparison of treatment strategies and intervention content for all those randomised to MAC or TAU during the 12-month follow-up period post randomisation for the cost-effectiveness. The TRS is a non-validated measure collecting clinicians' report monthly for each young person and is used to record specific intervention strategies (e.g., goal setting, supportive listening, family therapy) provided to young

people and/or parents/families during sessions, and the frequency with which they are provided. We have revised it following feedback from clinicians in the PDG.

Routinely Collected Data

Given that the utilisation of core mindfulness skills in adults is maintained, and often increases, after the completion of MBCT (Farb et al., 2018), we will explore attitudes to data linkage to support longer-term follow up. Specifically, we will seek permission to link trial data to education data from schools, apprenticeships, and higher education to explore attendance, attainment, and exclusion, plus Hospital Episode Statistics and the Mental Health Dataset to explore future health service contacts.

Qualitative Analyses to Investigate the Experience of the Intervention

We will use qualitative analyses to explore young people's and carer's experience of the intervention more widely. As described above, previous research in young people has used varying degrees of practice requirements and a major focus of this qualitative analysis will therefore be on factors influencing such engagement and its relationship with subjectively experienced dynamics of change.

We will investigate young people and carer's views on:

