We will test, in young people and in parent/carers, whether the degree to which they engage in practice during the intervention is related to changes in decentring and mindfulness skills over the period of the intervention, and to levels of symptoms measured using the SMFQ. We assume that regular practice is necessary for effective development of the treatment-related skills that serve to reduce depression and will test the hypothesis that effects of practice on depressive symptoms during follow-up are mediated through changes in decentring and general mindfulness skills during the intervention, both in young people and in adults who participated in MAC. We will use similar methods to those described above for the other mediation modelling, but will just model data from the individuals in the MAC arm, i.e., those for whom we can measure engagement in practice.

Mediation analysis methods

Mediation will be evaluated using structural equation modelling and/or causal mediation analysis methods adjusting for the stratification variables and baseline measures where appropriate (i.e., adjusting for baseline measures of mediator and outcome in mediator models (Dunn et al., 2015) and using appropriate modelling methods (i.e., temporally ordered mediator and outcome, longitudinal models where appropriate). Given previous research on MBCT that has provided evidence for the importance of acquisition of therapy-related skills across the intervention period (C. Crane et al., 2014), as well as their refinement and continued utilisation after the end of the intervention (Segal et al., 2019), we will run separate sets of analyses to test mediation of outcome at the end of intervention and at the end of follow-up. We may explore the extension of this methodology to repeated measures/AUC models. If we find significant baseline moderators of treatment effect, we may explore whether there is mediated moderation (Dunn et al., 2015; Muller et al., 2005). All mediation models will use raw mediator and outcome scores adjusted for baseline scores, rather than change scores (Landau et al., 2018).

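### Other therapy received after randomisation can confound the mediator–SMFQ path, and the adjustment set stated in Section 17 cannot remove it

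*Protocol*

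**What the plan says.** **Therapy by arm.** The opening of Protocol Section 13 says that "our PDG indicated that YP in the MAC arm received less mental health intervention than those randomised to TAU", "and we expect to find similar results during the current study". The Summary of TAU in the same section repeats the pilot finding ("The TAU arm received more treatment, including Family Therapy and Interpersonal Therapy than those in the MAC arm") and adds that clinicians often moved to less frequent contacts for those allocated to MAC. No amounts are given.

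**Control of usual care.** Summary of TAU: "We will not be controlling or changing the participants' TAU, we have requested from sites that both arms be offered their usual care".

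**Mediation models.** Section 17, Mediation analysis methods, uses structural equation modelling and/or causal mediation methods, "adjusting for the stratification variables and baseline measures where appropriate (i.e., adjusting for baseline measures of mediator and outcome in mediator models". It also asks for temporal ordering of mediator and outcome, with separate analyses at the end of intervention and at the end of follow-up. Therapy received after randomisation is not mentioned. Relationship quality (PARS) is among the mediators.

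**Data on other therapy.** Section 14 has clinicians complete the Treatment Recording Sheet (TRS) monthly for each young person, "to allow for comparison of treatment strategies and intervention content for all those randomised to MAC or TAU" over the 12 months. The stated purpose is the cost-effectiveness work. Nothing links the TRS to Section 17.

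**The concern.** An indirect effect is the product of an arm-to-mediator path and a mediator-to-outcome path. Randomisation protects only the first. The second is observational, and a variable that moves both mediator and symptoms will bias it unless it is dealt with.

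Other psychological therapy is an obvious candidate. Family therapy could improve perceived relationship quality and also lower SMFQ; other therapies could act on rumination or emotion regulation and on SMFQ. This therapy is delivered after randomisation, so baseline measures cannot stand in for it. Because the protocol expects allocation to change it, it is also a treatment-affected confounder. Standard natural-effect mediation assumes there is none, so choosing causal mediation methods does not by itself solve the problem.

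At stake are the answers to the mechanism questions in Section 9: whether MAC works through its intended psychological mechanisms, and whether change transfers across the dyad. Mediation could be declared for an inert mediator, or a real MAC effect on relationship quality could be hidden because the TAU arm had more family therapy.

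**Working it through.** The plan has no figure to reproduce here: it gives neither the amount of therapy by arm nor any path size. Every path below is an assumption, chosen to show direction and a plausible range.

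**Step 1. Large-sample bias.** Let A be arm, U other therapy, M the mediator (higher is better) and Y symptoms (lower is better), with all residual SDs equal to 1:

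- U = d·A + error, where d is displacement (negative: less therapy in the MAC arm)
- M = 0.4·A + u·U + error
- Y = m·M − 0.3·U + error

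Within arms, cov(M, U) = u and var(M) = 1 + u². Regressing Y on A and M without U therefore gives

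- mediator slope = m + u·(−0.3)/(1 + u²)
- arm-to-mediator path = 0.4 + u·d

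Displacement d does not appear in the slope. With m = −0.3:

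- u = 0.2: −0.3 − 0.06/1.04 = −0.358, and 0.358/0.300 = 1.19, an overstatement of 19%.
- u = 0.4: −0.3 − 0.12/1.16 = −0.403, and 0.403/0.300 = 1.34, about one third.
- u = 0: no bias in the slope or the indirect effect.

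Displacement acts elsewhere. With u = 0.4 the arm-to-mediator path is 0.40 at d = 0, 0.4 − 0.12 = 0.28 at d = −0.3, and 0.4 − 0.24 = 0.16 at d = −0.6. This is the masking.

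At u = 0.4 and d = −0.3:

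- m = −0.3: estimated indirect effect 0.28 × −0.403 = −0.113, against a true 0.28 × −0.3 = −0.084.
- m = 0: spurious indirect effect 0.28 × −0.103 = −0.029. With no displacement it is larger: 0.40 × −0.103 = −0.041.

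Where therapy bypasses the mediator (u = 0), displacement falls in the direct effect and counts against MAC: −0.3 × −0.3 = +0.09 at d = −0.3, and −0.3 × −0.6 = +0.18 at d = −0.6. Simulation with 1,000,000 participants per setting agrees with these formulas to within about 0.005.

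**Step 2. False mediation at the trial's size.** 240 per arm with 20% attrition leaves 240 × 0.8 = 192 per arm. Assumptions: MAC raises the mediator by 0.5 SD; the mediator has no effect on SMFQ; mediator and SMFQ have unit variance within arms; both paths must be significant at 5%; 3,000 trials per setting. Percentage of trials declaring mediation with therapy left out:

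| Therapy to mediator, therapy to SMFQ | No displacement | −0.3 SD | −0.5 SD |
|---|---|---|---|
| 0.2, −0.2 | 13.2 | 13.1 | 11.4 |
| 0.3, −0.2 | 20.5 | 20.9 | 19.0 |
| 0.3, −0.3 | 41.9 | 40.3 | 38.9 |
| 0.4, −0.3 | 64.2 | 61.4 | 53.3 |

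With therapy in the model the rate is 4% to 6%. Scaling matters: a run over displacements of 0.3 to 0.5 SD with the same nominal paths gave 11% to 52%. Neither run includes therapy-group clustering or missing data.

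The first column is the informative one. The error is present with no displacement and tends to fall as displacement grows. In the last row the spurious indirect effect goes from 0.5 × (0.4 × −0.3) = −0.060 to (0.5 − 0.2) × −0.12 = −0.036.

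**The case against.** **It is a matter for the SAP.** Section 16 defers statistical detail to a SAP that is not shown, and Section 17 leaves the choice of method open. This has weight: the missing sensitivity analysis alone would be no finding. But Section 17 does state an adjustment set, and its "adjusting for the stratification variables and baseline measures where appropriate" covers baseline quantities only. It passes over a variable that the same document predicts will differ by arm and already plans to record.

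**It is ordinary confounding.** Any trial with uncontrolled co-treatment has this problem, as the no-displacement column shows. That stands. A reader might infer that effects of displaced usual care are credited to MAC's mediators; neither the text nor the arithmetic supports this. Displacement lowers the arm-to-mediator path or falls in the direct effect.

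**The sizes are invented.** True. If therapy does not move a given mediator, that indirect effect is unbiased. If clinicians give more therapy to those who are more unwell, the bias could change in size or sign.

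**There is no contradiction about usual care.** A reader might set "we have requested from sites that both arms be offered their usual care" against the expectation of less therapy in the MAC arm. One concerns what is offered and the other what is received, and both can be true.

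**Adjustment may do harm.** Also fair. Entering therapy as an ordinary covariate is not a full remedy, because therapy is affected by arm and may respond to symptoms. This argues for a sensitivity analysis and against replacing the main model.

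**Conclusion.** The point holds for the mechanism analyses only. Other therapy after randomisation is uncontrolled, expected to differ by arm, and plausibly related to both mediators and SMFQ; the stated adjustment set cannot remove the resulting confounding. The risk of false mediation comes from within-arm variation in therapy. Displacement adds possible masking and makes the confounder depend on allocation.

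No size can be derived from the protocol. The 19% to one-third overstatement and the 11% to 64% false-mediation range rest on assumed linear paths in which therapy always helps and varies at random within arms. They show that the problem could matter and do not estimate it for this trial.

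A reader might also infer that the primary result is biased. It is not: the intention-to-treat comparison remains a valid contrast of the two policies as delivered. Only its reading needs care, since a null result could reflect MAC partly replacing other therapy.

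**What to change.** In Section 17, or in the SAP with a reference from Section 17, pre-specify a sensitivity analysis:

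- Report each indirect effect with and without TRS-recorded therapy.
- Model therapy as a post-randomisation variable affected by arm (arm to therapy, therapy to mediator, therapy to SMFQ), or use interventional indirect effects.
- Use therapy recorded before the mediator is measured. For the 12-month models also consider therapy after T1, recognising that it may itself follow from the mediator.
- Show family and interpersonal therapy separately for the relationship-quality models if numbers allow.
- State the assumptions: therapy may respond to symptoms, and the TRS is non-validated and may have missing months.

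Also present therapy received by arm beside the primary result, so that readers can see how far MAC added to usual care or replaced it.

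The cost is wording and extra modelling on data already being collected, with some loss of precision in the adjusted indirect effects. No change to treatment, visits or sample size is needed.

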14. OUTCOMES

Outcome measures (**Appendices j and k**) were chosen in close collaboration with young people and parents to reflect target psychopathology, key therapeutic components, and clinical processes. Participants will need to have completed all intake and baseline measures before they are randomised.

- Young people will then complete the Short Mood and Feelings Questionnaire SMFQ; (Angold et al., 1995) every fortnight for 12 months.
- Parents/carers will then complete the Generalised Anxiety Disorder GAD-7; (Spitzer et al., n.d.-a) every fortnight for 12 months.

The full complement of measures as listed in **Table 5** will be completed by both groups 14 weeks and 12 months after randomisation. If participants withdraw from treatment, we will continue to request outcome measures from them for the 12-month follow-up, unless they choose to formally withdraw from the trial completely.

Timepoint Data Collected Young People Parent/Carer T1: T2: Construct **TO:** Completed Completed 3.5m 12m B/L F/U F/U Eligibility CRIES-8 (Perrin et al., **PTSD** screen At intake assessment 2005) 33 item MFQ (COSTELLO & ANGOLD, Current low mood At intake assessment 1988; Daviss et al., 2006) **Baseline Outcomes Current depression and** RCADS 25 (Ebesutani et Х anxiety severity al., 2012) Past trauma and YCAS (Schlechter et al., YCAS (Schlechter et al., Х adversity 2021) 2021) Own and child's Race/ethnicity, family, current living situation^c Child's DOB, gender, current medication for Respondent anxiety or depression, Х Background past treatment for depression and anxiety^c Own occupation, personal history of depression, education background Site option Face-to-face or remote Х

Table 5: Outcome Measures

Primary outcome					
YP Depression	SMFQ (Angold et al., 1995)		Repeate intervals follow-u	d at 2 wee throughc p	ekly out
Secondary outcomes					
P/C Depression		PHQ (Kroenke et al., 2009b)	Repeated at 2 weekly intervals throughout follow-up		
YP Depression	33 item MFQ (COSTELLO & ANGOLD, 1988; Daviss et al., 2006)		х	x	x
Anxiety	RCADS 25 (Ebesutani et al., 2012)	GAD-7 (Spitzer et al., n.db)	х	х	х
Quality of Life ^a	EQ-5D-5L (Devlin et al., 2018b)	EQ-5D-5L (Devlin et al., 2018b)	et al., X X		х
Coping	1 bespoke question	1 bespoke question	Х	Х	Х
Parent – young people relationship quality ^b	PARS (Burke et al., 2021)	PARS (Burke et al., 2021)	х	х	х
Health Economics Measures					
Services and personal costs		Child's resource use bespoke questionnaire ^c	х	х	х
Quality of Life ^a	EQ-5D-5L (Devlin et al., 2018b)	EQ-5D-5L (Devlin et al., 2018a)	х	х	х
Mediators					
Decentring and wider mindfulness	CHIME-A (C. Johnson et al., 2017)	CHIME-S (Karl et al., 2024)	х	х	х
Self-Compassion	SCS-SF (Raes et al., 2011)	SCS-SF (Raes et al., X 2011)		х	х
Emotion Regulation	ERQ (Gross & John, 2003)	ERQ (Gross & John, 2003)	х	х	х
Rumination	Rumination sub-scale of CRSQ (Abela et al., 2002)	Brooding and Reflection sub-scales of RSS (Treynor et al., 2003)	х	х	х
Parent – young people relationship quality ^b	PARS (Burke et al., 2021)	PARS (Burke et al., 2021)	х	х	х
Experience of MAC	Qualitative interviews with participants	ialitative interviews with a sub-set of MAC X			х
Type and duration of mindfulness practice	Weekly records of mindfulness practice (MAC arm only)	Weekly records of mindfulness practice (MAC arm only)			

recent meditation recent meditation X X X X practice	Bespoke question about recent meditationBespoke question about recent meditationXXpracticepracticeXX	х
--	--	---

^a Quality of life measured using the EQ-5D-5L is both a secondary outcome and used in the health economic analysis.

^b PARS is both a secondary outcome and a mediator.

^c In situations where a parent/carer does not consent to their own involvement in the study, we would ask the young person to complete the information about their background, service and personal cost use.

Peterborough NHS Foundation Trust

Adolescents and carers using mindfulness Therapy To END depression

Figure 5: Schematic diagram of the trial design, procedures, stages, and data collection

WP3+4 Study Protocol, Version 1.3, 20.6.24

Primary outcome measure

The **primary clinical outcome will be the mean difference in depression** measured using the Short Moods and Feelings Questionnaire (SMFQ); (Angold et al., 1995) over the 12 months follow-up period using an Area Under the difference Curve (AUC) analysis of the fortnightly and follow up measures, as this better reflects the maintenance of recovery than a single data point at 12 months. We selected the SMFQ (Angold et al., 1995) as our primary outcome as it is recommended to monitor response to treatment by the National Institute of Clinical Excellence in Health and Social Care guidance (NICE, 2019) and has been shown to be sensitive to improvement in previous UK-based RCTs of interventions for depression in young people (Goodyer et al., 2008, 2017; Stallard et al., 2012).

Baseline moderators of treatment effects

To gather important information about participants' backgrounds we will ask about the following characteristics:

- the severity of depression and/or comorbid anxiety at baseline as measured by the RCADS (Ebesutani et al., 2012),
- exposure to childhood trauma as measured by the YCAS (Schlechter et al., 2021)
- ethnicity,
- age group (15 to 16 versus 17 to 18).

Youth and Childhood Adversity Scale (YCAS) (Schlechter et al., 2021)

The YCAS (Schlechter et al., 2021) is a 13-item measure of early adversity, assessing the experience (yes/no) and severity of adverse events (7-point Likert scale: 1-Not at all traumatic, 4-Somewhat traumatic, 7-Extremely traumatic). Total scores can be generated to reflect the total number of adverse events experienced or also incorporate the severity of these events (higher scores indicate greater number of experiences or severity of early adverse events, respectively). Both approaches yield a reliable, valid, and psychometrically sound measure.

Secondary outcome measures

The secondary outcomes will be expressed as the mean differences between the MAC + TAU versus TAU arms at 14 weeks and 12 months post-randomisation.

Collected every fortnight:

Patient Health Questionnaire eight-item depression scale PHQ-8; (Kroenke et al., 2009a)

The PHQ-8(Kroenke et al., 2009a; Kroenke & Spitzer, 2002) evaluates 8 of the 9 DSM-IV depression diagnostic criteria, omitting the question about suicide and self-harm. Patients are asked how many days in the last 2 weeks they experienced different symptoms (0-1 days = 0, 2-6 days = 1, 7-11 days = 2, 12-14 days = 3). The maximum score is 24, with higher scores indicating greater symptom severity. Scores ≥10 are taken to signify clinical level major depression and when this cut off is used, sensitivity and specificity are both 88% (Corson et al., 2004; Kroenke et al., 2001; Kroenke & Spitzer, 2002). In line with the SMFQ, this will be analysed over the 12 months follow-up period using an Area Under the difference Curve (AUC), as this better reflects levels of depression throughout the period rather than one single data point.

Collected at T0, T1 and T2 only:

Revised Child Anxiety and Depression Scale Short Form RCAD-SF; (Ebesutani et al., 2012)

The RCAD-SF (Ebesutani et al., 2012) is a 25-item questionnaire that measures anxiety (15 items) and depression (10 items). Items are scored on a 4-point Likert scale (Never, Sometimes, Often or Always) with higher scores indicating greater levels of psychopathology. Both the depression and anxiety sub-scales show good internal and external validity with good reliability in both a clinical and school-based sample (Ebesutani et al., 2012). The RCADS will be used as a Baseline Moderator (T0) to measure depression severity for stratification, and also be used at T1 and T2 as a secondary outcome measure for anxiety. It will not be used to analyse depression outcomes in young people, as that is measured using the SMFQ as the primary outcome.

Moods and Feelings Questionnaire 33 MFQ 33; (COSTELLO & ANGOLD, 1988; Daviss et al., 2006) The MFQ is a 33-item self-report scale designed to assess depressive symptoms in children and adolescents aged 8 to 18 years. It covers various domains of depression, including mood, anhedonia, and cognitive symptoms. Respondents rate each item based on how they have been feeling or acting recently, with choices ranging from 0 to 2. The total score ranges from 0 to 66, with higher scores indicating greater levels of depressive symptoms. A cutoff score of 20 or above is often used to indicate clinically significant depressive symptoms (Cooper & Goodyer, 1993). The MFQ has demonstrated good internal consistency (α = .89 to .95) and test-retest reliability (r = .79 to .91). Additionally, it has been shown to have good convergent and discriminant validity when compared with other measures of depression (COSTELLO & ANGOLD, 1988; Daviss et al., 2006).

Generalized Anxiety Disorder 7 GAD 7; (Spitzer et al., n.d.-a)

The GAD-7 (Spitzer et al., n.d.-a) is 7-item scale measuring symptoms of anxiety and worry. Items are rated on a 4-point Likert scale (0-3; maximum score 21), with higher scores reflecting greater symptom severity. Scores \geq 10 indicate clinical levels of anxiety. The scale is reported to have excellent internal consistency (α = .89) and good convergent validity (S. U. Johnson et al., 2019; Löwe et al., 2008). Sensitivity and specificity are between 89-74% and 82-54%, respectively when a cut off of 10 is used (Beard & Björgvinsson, 2014).

Ability to 'cope'

Following consultation with our Patient and Public Intervention (PPI) group, we will ask a bespoke question about participants' perception of their ability to cope with life on a 5-point Likert scale.

Parent-Adolescent Relationship Scale PARS; (Burke et al., 2021).

Critical Dimensions of the parent–adolescent relationship will be assessed from multiple perspective using the Parent Adolescent Relationship Scale (Burke et al., 2021). The PARS is a 20-item measure that comprises three subscales: connectedness, shared activities, and hostility. Initial research has demonstrated good discriminant and convergent validity (Burke et al., 2021).

Mediators

Collected at T0, T1, T2:

PARS (Burke et al., 2021) (above) is also a mediator.

CHIME-S (Karl et al., 2024)/CHIME A (C. Johnson et al., 2017)

The Comprehensive Inventory of Mindfulness Experiences CHIME; (Karl et al., 2024) is an established selfreport questionnaires available in parallel versions for adults (Bergomi et al., 2014; S. Wilkinson et al., 2023) and adolescents (C. Johnson et al., 2017). The CHIME-S and CHIME-A cover mindfulness as a complex construct consisting of the following facets (subscales):

• Awareness of Internal Experience,

- Awareness of External Experience,
- Acting with Awareness,
- Accepting and Nonjudgmental Orientation,
- Decentring and Nonreactivity,
- Openness to Experience,
- Relativity of Thoughts, and
- Insightful Understanding.

They will be administered at all main trial assessment points for all individuals, young people, and carers.

Self-Compassion Scale Short Form SCS-SF; (Raes et al., 2011)

The SCS-SF (Neff, 2016; Raes et al., 2011) is a 12 item self-report measure of self-compassionate responding in the event of failure and distress. Items are rated on a five-point scale from 1 (almost never) to 5 (almost always). The measure has excellent internal consistency (α = .89) as well as good convergent, divergent, content and face validity (Raes et al., 2011).

Emotion Regulation Questionnaire ERQ; (Gross & John, 2003)

The ERQ (Gross & John, 2003) uses a 10-item scale to measure 2 different emotion regulation strategies: cognitive reappraisal (6 items) and expressive suppression (4 items). Items are rated on a 7-point Likert scale from 1–7, with higher scores indicating greater agreement with items. The cognitive reappraisal facet negatively predicts psychological distress and alexithymia, whilst expressive suppression is positively correlated with these characteristics (Preece et al., 2020). Across samples, the two ERQ facets show adequate to excellent internal consistency (cognitive reappraisal α = .89-.90; expressive suppression α = .76-.80 (Preece et al., 2020)).

Ruminative Responses Scale Brooding and Reflection Sub-Scales RRS-BR; (Treynor et al., 2003) Rumination will be assessed using the Ruminative Responses Questionnaire (Treynor et al., 2003) at all points of assessment on all individuals in the trial. The full RRS (Treynor et al., 2003) is a 22-item scale to measuresymptom focused, self-focused and cause-focused responses to depressive mood. Since depressive mood is being measured elsewhere, we will only use the brooding and reflection sub-scales which comprise 10 items in total. Items are rated from 1 (almost never) to 4 (almost always). Internal consistency is excellent (α = .90), and test-retest reliability is adequate (r = .67;(Treynor et al., 2003).

Children's Response Styles Questionnaire Rumination Sub-Scale CRSQ-R; (Abela et al., 2002)

The full CRSQ (Abela et al., 2002) is 25-item scale measuring responses to depressive symptoms. It includes 3 scales (ruminative, distractive, and problem-solving responses) which are scored individually by taking the mean (1-4) of items from that scale. Higher scores indicate a higher likelihood of responding in a given manner to depressive symptoms. Internal consistency across subscales is moderate to high (α = .51-.84) and scores are predictive of level of depressive symptoms, self-control, and perceived helplessness, (Abela et al., 2002; Treynor et al., 2003). Since our focus is on rumination, we will only use the 13 item sub-scale that measures rumination.

Collected weekly during the 8-week intervention (MAC arm only)

Measuring engagement with mindfulness practice

Participants will be asked to record their daily mindfulness practice, either directly via the app or on paper diary cards. We will measure number of times both formal and informal mindfulness has been practiced as well as recording which practices were used. Whilst self-report will be the primary source of this data, we will

cross reference this with metrics recorded directly via the app, for example, the dates, duration, and frequency of log-ons as well as how often each audio recorded mindfulness practice was played.

Health Economic Measures

Cost components included in the health economic analysis will comprise:

- Detailed costs of the MAC intervention,
- Other NHS and social service use during the 12-month within-study period, including:
 - CAMHS, primary care, social care, and community care contacts,
 - \circ prescribed medications,
 - hospital inpatient admissions and outpatient attendances,
 - School attendance and other education-related contacts
- Informal care costs incurred by participants, parents and carers and families, including time taken off work.

The intervention costs will comprise the costs of:

- training the trainers,
- staff time to deliver MAC classes and pre-class orientation interviews,
- non-staff costs associated with delivery of MAC classes (e.g., life or virtual room hire),
- the costs of delivering the app, and
- provision of information materials for participants and families.

The volume of resource use for the non-intervention cost components will be measured in the trial using a bespoke retrospective questionnaire based on a modified version of the Client Service Receipt Inventory, completed by participants for a 12-month period at baseline, 14 weeks, and 12-months post-baseline for each individual participant. These questionnaires will cover the previous 3-month period at baseline and 3 months, and the previous 9-month period at 12 months.

When parents/carers have consented to take part we will ask them to complete this information on behalf of their child. If the young person's parent/carer has not consented for their own involvement, then we will ask the young person themselves to complete this questionnaire.

EQ-5D-5L Quality of Life (Devlin et al., 2018a)

The EQ-5D-5L (Rabin & Charro, 2001) describes health status in 5 health dimensions, with 5 levels of each. The patient reports their present health state by ticking the level of each dimension that currently applies to them. They then rate their current health state from 0-100 (best possible health state). This measure has good convergent and divergent validity with other health questionnaires (J. A. Johnson & Pickard, 2000).

Treatment Recording Sheet TRS; (Bearsley-[name] et al., 2008)

We will also measure public and charitable sector services accessed and health-related quality of life for both young people and carers for economic evaluation. Researchers will support practitioners to complete the revised TRS (Bearsley-[name] et al., 2008) (**Appendix L**) for any other therapy or psychological intervention provided, to allow for comparison of treatment strategies and intervention content for all those randomised to MAC or TAU during the 12-month follow-up period post randomisation for the cost-effectiveness. The TRS is a non-validated measure collecting clinicians' report monthly for each young person and is used to record specific intervention strategies (e.g., goal setting, supportive listening, family therapy) provided to young

people and/or parents/families during sessions, and the frequency with which they are provided. We have revised it following feedback from clinicians in the PDG.

Routinely Collected Data

Given that the utilisation of core mindfulness skills in adults is maintained, and often increases, after the completion of MBCT (Farb et al., 2018), we will explore attitudes to data linkage to support longer-term follow up. Specifically, we will seek permission to link trial data to education data from schools, apprenticeships, and higher education to explore attendance, attainment, and exclusion, plus Hospital Episode Statistics and the Mental Health Dataset to explore future health service contacts.

Qualitative Analyses to Investigate the Experience of the Intervention

We will use qualitative analyses to explore young people's and carer's experience of the intervention more widely. As described above, previous research in young people has used varying degrees of practice requirements and a major focus of this qualitative analysis will therefore be on factors influencing such engagement and its relationship with subjectively experienced dynamics of change.

We will investigate young people and carer's views on:

